APPENDIX 7. MEDICATIONS TO BE USED WITH CAUTION

Sensitive CYP2C9 Substrates or CYP2C9 Substrates with Narrow Therapeutic Index

celecoxib¹

Phenytoin²

Warfarin²

¹ Sensitive substrates: Drugs that exhibit an AUC ratio (AUC_i/AUC) of 5-fold or more when co-administered with a known potent inhibitor.

² Substrates with narrow therapeutic index (NTI): Drugs whose exposure-response indicates that increases in their exposure levels by the concomitant use of potent inhibitors may lead to serious safety concerns (e.g., Torsade de Pointes).

Strong CYP2C8 Inhibitors

gemfibrozil

APPENDIX 8. EASTERN COOPERATIVE ONCOLOGY GROUP (ECOG) PERFORMANCE STATUS

Grade	Description
0	Fully active, able to carry on all pre-disease performance without restriction
1	Restricted in physically strenuous activity but ambulatory and able to carry out work of a light or sedentary nature, e.g., light housework, office work
2	Ambulatory and capable of all self-care but unable to carry out any work activities. Up and about more than 50% of waking hours
3	Capable of only limited self-care, confined to bed or chair more than 50% of waking hours
4	Completely disabled. Cannot carry on any self-care. Totally confined to bed or chair
5	Dead

As published by ([Oken et al 1982](#)). Eastern Cooperative Oncology Group, Robert Comis M.D.,

APPENDIX 9. EVALUATION OF RESPONSE ACCORDING TO CA-125

The text below was obtained from the following reference:

Gordon John Sampson Rustin, etc. Definitions for Response and Progression in Ovarian Cancer Clinical Trials Incorporating RECIST v1.1 and CA-125 Agreed by the Gynecological Cancer Intergroup (GCIIG). *Int J Gynecol Cancer*. 2011;21: 419-423.

Definition of Response:

A CA-125 response is defined as at least a 50% reduction in CA-125 levels from a pretreatment sample. The response must be confirmed and maintained by using the next scheduled CA-125 data (at least 28 days). Patients can be evaluated according to CA-125 only if they have a pretreatment sample that is at least twice the upper limit of the reference range and within 2 weeks before starting the treatment.

To calculate CA-125 responses accurately, the following rules apply:

- Intervening samples and the 28-day confirmatory sample must be less than or equal to (within an assay variability of 10%) the previous sample.
- Variations within the reference range of CA-125 levels will not interfere with the response definition.
- For each patient, the same assay method must be used, and the assay must be tested in a quality control scheme.
- Patients are not evaluable by CA-125 if they have received mouse antibodies (unless the assay used has been shown not to be influenced by human anti-mouse antibody^{4, 5}) or if there has been medical and/or surgical interference with their peritoneum or pleura during the previous 28 days (e.g., paracentesis). If assessing therapy that includes 2 treatment modalities for relapse (e.g., surgery and chemotherapy), any CA-125 response results from both treatment modalities. CA-125 cannot distinguish between the effects of the 2 treatments.

The date when the CA-125 level is first reduced by 50% is the date of the CA-125 response. To calculate response, an intent-to-treat analysis should be used that includes all patients with an initial CA-125 level of at least twice the upper limit of the reference range as eligible and evaluable. In addition, as a separate analysis, those patients who have a CA-125 response and whose CA-125 level falls to within the reference range can be classified as CA-125 complete responders. In [Appendix 9 Table 1](#) and [Appendix 9 Table 2](#) CA-125 is stated as normalized or normal, means within the reference range. Patients who have a fall of CA-125 to within the reference range but whose initial CA-125 was less than twice the upper limit of the reference range have not had a CA-125 response and cannot therefore be classified as a CA-125 complete responder.

Reporting of response according to GCIIG criteria that integrate CA-125 response with RECIST v1.1 is shown in [Appendix 9 Table 1](#) and [Appendix 9 Table 2](#).

Appendix 9 Table 1: Evaluation of best overall response in patients without initial measurable disease and who are evaluable by CA-125

CA-125	Nontarget Lesions*	New Lesions	Overall Serological Response	Best Response for This Category Also Requires
Response and Normalized	CR	No	CR	Confirmed and maintained for at least 28 days
Response	Non-progressive disease	No	PR	
Normalized but no response	Non-CR/Non-progressive disease	No	SD	
Non-PR/non-progressive disease	Non-progressive disease	No	SD	
Progressive disease	Any	Yes or No	progressive disease	
Any	progressive disease †	Yes or No	progressive disease	
Any	Any	Yes	progressive disease	

1. *Nontarget lesions include ascites and peritoneal thickening, which are not measurable according to RECIST.
2. †Unequivocal progression in nontarget lesions may be accepted as disease progression.
3. CR: Complete response; PR: partial response; SD: stable disease.

Appendix 9 Table 2: Best overall response in patients with measurable disease and who are also evaluable by CA-125

Target Lesion*	Nontarget Lesions†	New Lesions	CA-125	Overall Best Response	Best Response for This Category Also Requires
CR	CR	No	Normal	CR	Best RECIST v1.1 response for CR and PR also required it to be confirmed and maintained for at least 28 days if response is primary end point
CR	Non-CR Non-progressive disease	No	Not progressive disease	PR	
CR	CR	No	PR but not normal	PR	
CR	NE	No	PR	PR	
PR	Non-progressive disease or NAE	No	Not progressive disease	PR	
NAE	Non-progressive disease	No	PR	PR	
Progressive disease or New >28 days from CA-125 PR‡			PR	PR	
SD§	Non-progressive disease	No	PR	PR	
SD§	Non-progressive disease or NAE	No	Not PR and not progressive disease	SD	
Progressive disease or New >28 days from CA-125 PR‡			PR	progressive disease	
Progressive disease	Any	Yes or No	Any	progressive disease	
Any	progressive disease	Yes or No	Any	progressive disease	
Any	Any	Yes	Any	progressive disease	
Any	Any	Yes or No	progressive disease	progressive disease	

- *Target lesions include up to 5 measurable lesions (2 per organ) as defined by RECIST v1.1.
- †Nontarget lesions include ascites and peritoneal thickening which are not measurable according to RECIST v1.1.
- ‡Patients who have a CA-125 response that occurs more than 28 days from PD according to RECIST v1.1 are considered a PR, according to best response, but PD if the RECIST v1.1 PD is within 28 days of CA-125 response.
- §The protocol should specify the minimum time interval between 2 measurements for classification as stable disease. NE, Not evaluated; NAE, not all evaluated.

APPENDIX 10. PROSTATE CANCER CLINICAL STUDIES WORKING GROUP 2 (PCWG2) CRITERIA TO GUIDE ASCRIBING DISEASE RESPONSE

The table below is modified from the following reference:

Variable	PCWG2 (2007)
PSA	
On this study serial PSA measurements will be done every 8 weeks \pm 7 days after the first dose of Pamiparib in the first year and every 9 weeks \pm 7 days afterwards. Increases and decreases will be tracked in order to assess disease response. The PSA readings on its own will not be used to define progression in this protocol. PSA response and PSA progression will be defined according to the consensus guidelines of the PCWG 2:
 
 • PSA partial response is defined as a \geq 50% decline in PSA from Cycle 1 Day 1 (baseline) PSA value. This PSA decline much be confirmed to be sustained by a second PSA value obtained 4 or more weeks later. • PSA progression date is defined as the date that a \geq 25% increase and an absolute increase of \geq 2 ng/mL above the nadir is documented, which is confirmed by a second consecutive value obtained 4 or more weeks later. The first PSA reading will be obtained at week 12. 
Duration of PSA Response: Duration of PSA response is calculated from the time the PSA value first declines by at least 50% of the Cycle 1 Day 1 (baseline) value that has been confirmed by a second value until the time there is an increase of 25% of PSA nadir, provided the absolute increase is at least 2 ng/mL. The increase must be confirmed by a second consecutive measurement that is at least 25% above the nadir. If the PSA never shows a 25% increase over the nadir value, then the patient will be assessed at the last PSA measurement.

Target Lesions
	
Nodal or visceral progression sufficient for study entry independent of PSA measurable lesions not required for entry.
 
Use RECIST to record soft-tissue (nodal and visceral) lesions as target or non-target.
 
Only lymph nodes ≥ 2 cm in diameter should be used to assess for a change in size.
 
Record presence of nodal and/or visceral disease separately.
 
Progression at any scheduled reassessment ≥ 12 weeks does not need to be confirmed.


Bone
	
≥ 2 new lesions at the first scheduled reassessment ≤ 13 weeks from Cycle 1 Day 1 compared with baseline must be confirmed by a second scan performed 6 or more weeks later.
 
Confirmatory scans should show an additional 2 new lesions compared to the first post-treatment scan (i.e. a total of ≥ 4 new lesions compared with the baseline bone scan).
 
Confirm ambiguous results by other imaging modalities (e.g., CT or MRI).
 
Investigators are highly encouraged to maintain the patient's treatment with study medication unless progression is confirmed.
 <hr/> 
≥ 2 new lesions at the first scheduled reassessment > 13 weeks from Cycle 1 Day 1 compared with baseline must be confirmed by a second scan performed 6 or more weeks later.
 
Confirmatory scans should confirm the presence of the 2 new lesions compared to the baseline scan. (i.e. a total of ≥ 2 new lesions compared with the baseline bone scan).
 
Confirm ambiguous results by other imaging modalities (e.g., CT or MRI).
 
Investigators are highly encouraged to maintain the patient's treatment with study medication unless progression is confirmed.

CT: computed tomography; MRI: magnetic resonance imaging; PCWG2: Prostate Cancer Clinical Trials Working Group 2;
 PET: positron emission tomography; PSA: prostate-specific antigen; PSA-DT: PSA doubling-time;
 RECIST: Response Evaluation Criteria in Solid Tumors

CTC-HRD-negative or CTC-HRD-	circulating tumor cells negative for homologous recombination deficiency per Epic Sciences assay
CTC-HRD-positive or CTC-HRD+	circulating tumor cells positive for homologous recombination deficiency per Epic Sciences assay
CYP	cytochrome P450
DOR	duration of response
ECG	electrocardiogram
ECOG	Eastern Cooperative Oncology Group
eCRF	electronic case report form
EDC	electronic data capture
EOT	End-of-Treatment (Visit)
FDG	fluorine-18 [F-18]fluorodeoxyglucose
HBV	hepatitis B virus
HCV	hepatitis C virus
HRD	homologous recombination deficiency
IC ₅₀	half-maximal inhibition concentration
ICF	informed consent form
IEC	Independent Ethics Committee
IRB	Institutional Review Board
IRC	Independent Review Committee
mCRPC	metastatic castration-resistant prostate cancer
MDRD STUDY EQ	Modification of Diet in Renal Disease study equation
MDS	myelodysplastic syndrome
MRI	magnetic resonance imaging

Abbreviation	Definition
NCI-CTCAE	National Cancer Institute-Common Terminology Criteria for Adverse Events
NE	not evaluable
ORR	objective response rate
OS	overall survival
PAR	poly (ADP-ribose)
PARP	poly (ADP-ribose) polymerase
PCWG3	Prostate Cancer Clinical Trials Working Group 3
PD	progressive disease
PET	positron-emission tomography
PK	pharmacokinetic
PR	partial response
PSA	prostate-specific antigen
QTcF	QT interval with Fridericia's correction
RECIST	Response Evaluation Criteria in Solid Tumors
rPFS	radiographic progression-free survival
SAE	serious adverse event
SD	stable disease
TEAE	treatment-emergent adverse event
TMZ	Temozolomide
ULN	upper limit of normal
US or USA	United States or United States of America

1 INTRODUCTION

The purpose of this statistical analysis plan (SAP) is to describe the procedures and the statistical methods that will be used to analyze the efficacy and safety endpoints for protocol BGB-290-103: A Phase 1b Study to Assess the Safety, Tolerability, and Clinical Activity of BGB-290 in combination with Temozolomide (TMZ) in Subjects with Locally Advanced or Metastatic Solid Tumors. The focus of this SAP is for the planned primary, secondary and exploratory efficacy and safety analyses.

The analysis details for Pharmacokinetic (PK), Pharmacodynamics, Pharmacogenomics, and Biomarker analyses may not be fully described within this SAP. Separate analysis plans may be provided if applicable.

2 FOR THESE ANALYSES AND WILL BE ATTACHED TO THE CLINICAL STUDY REPORT STUDY OVERVIEW

This is an open-label, multi-center Phase 1b study to evaluate the combined use of pamiparib (also known as BGB-290), a poly (ADP-ribose) polymerase, e.g., PARP, inhibitor, with a deoxyribonucleic acid (DNA)-alkylating agent, TMZ, in subjects with locally advanced and metastatic solid tumors. The study consists of two phases, a dose escalation phase and a dose expansion phase. The dose escalation phase of the study will evaluate the safety, tolerability, preliminary efficacy, and PK in addition to determining the maximum tolerated dose (MTD) and/or maximum administered dose (MAD) for the combination. In the dose expansion phase of this study, the safety, preliminary efficacy and PK profile of the combination will be evaluated further. Preliminary biomarkers for efficacy will also be explored through both phases of the study.

Dose Escalation:

The dose escalation phase of the study consists of a modified 3+3 dose escalation scheme utilizing a fixed dose of BGB-290 in combination with escalating doses of TMZ. The following two arms were planned to undergo dose escalation independently:

- Arm A: TMZ will be administered once a day during Days 1 to 7 of each 28-day cycle (pulse dosing of TMZ)
- Arm B: TMZ will be administered once a day continuously during each 28-day cycle (continuous dosing of TMZ)

Dose Expansion:

The dose expansion phase of the study will further evaluate the safety and anti-tumor activity of BGB-290 in combination with TMZ at the dose and schedule that will be chosen based on all data available including the dose escalation phase. This dose expansion phase will enroll patients in 6 different cohorts according to indication and/or homologous recombination deficiency (HRD) status as follows:

- Cohort 1: HRD positive (HRD+) ovarian cancer;
- Cohort 2: HRD+ triple-negative breast cancer (TNBC);
- Cohort 3: HRD+ metastatic castration-resistant prostate cancer (mCRPC);
- Cohort 4: Extensive Stage Small Cell Lung Cancer;
- Cohort 5: Gastric/Gastroesophageal Junction Cancer; and
- Cohort 6: patients who have HRD+ nonsquamous non-small cell lung cancer (NSCLC), squamous NSCLC, esophageal cancer, squamous head and neck cancer or soft-tissue sarcomas. Enrollment into these cohorts will occur simultaneously and independently.

For the interim clinical study report (CSR), only cohort 1 to 5 will be included. All cohorts will be included in the final CSR.

3 STUDY OBJECTIVES

3.1 PRIMARY OBJECTIVE

- To determine the safety and tolerability of pamiparib (also known as BGB-290) when given orally in combination with temozolomide (TMZ) (pulsed and continuous)
- To determine the maximum tolerated dose (MTD) or maximum administered dose (MAD) for pamiparib combined with TMZ (pulsed and continuous)
- To select the recommended Phase 2 dose (RP2D) and schedule of pamiparib in combination with TMZ
- To determine the preliminary antitumor activity of pamiparib in combination with TMZ

3.2 SECONDARY OBJECTIVES

- To characterize the PK of BGB-290 and TMZ

3.3 EXPLORATORY OBJECTIVES

- To evaluate candidate biomarkers in tumor tissue and in peripheral circulation as potential makers of response, resistance, or disease progression

4 STUDY ENDPOINTS

4.1 PRIMARY ENDPOINTS

- Escalation: Incidence and nature of DLTs
- Escalation and Expansion: Incidence, nature, and severity of AEs, graded according to the National Cancer Institute Common Terminology Criteria for Adverse Events (NCICTCAE) v.4.03 and
- Objective response rate (ORR), as assessed using RECIST v1.1

4.2 SECONDARY ENDPOINTS

- Pharmacokinetic parameters of BGB-290 and TMZ, including but not limited to C_{trough}
- Time-to event- endpoints: e.g., duration of response (DOR), disease control rate (DCR), progression-free survival (PFS), and overall survival (OS)

4.3 EXPLORATORY ENDPOINTS

- Candidate predictive biomarkers, including, but not limited to, expression and mutations of genes in the DNA damage response pathway, and relationship to efficacy and resistance

5 SAMPLE SIZE CONSIDERATIONS

It is expected that approximately 250 patients will be enrolled in the entire study.

- **Dose Escalation Phase:** Approximately 50 patients may be enrolled. More patients may be enrolled if additional doses/schedules are to be evaluated based on emerging data.
- **Dose Expansion Phase:** Approximately 200 patients in total will be treated in 6 cohorts. Each cohort will enroll approximately 20-25 patients each and will be evaluated separately. Cohorts can be closed due to futility or clinical efficacy based on statistical evaluation or due to insufficient patient recruitment. Cohorts can be also further expanded based on emerging data.

A sample size of 20-25 patients in an expansion cohort will provide the half width of the 90% confidence interval of the ORR approximately 13% to 20% when the observed ORR is approximately 40%. Hence, the low bound is above 20%. This is considered adequate in the preliminary assessment of anticancer activity of pamiparib and TMZ combination therapy. The following [Table 1](#) gives the 90% confidence interval for estimated objective response rate between 36% to 41% for different sample sizes.

Table 1 Estimated Objective Response Rate and 90% Confidence Interval for 20-25 Patients

Sample Size	No. of Responders	Response Rate	90% Confidence Interval	
			Lower Limit	Upper Limit
20	8	40%	22%	61%
21	8	38%	21%	58%
	9	43%	24%	63%
22	8	36%	20%	56%
	9	41%	23%	60%
23	9	39%	22%	58%
	10	43%	26%	62%
24	9	38%	21%	56%
	10	42%	25%	60%
25	10	40%	24%	58%

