4.3. Expansion Cohorts

The dose expansion phase of the study will begin once the safety and tolerability have been reviewed for the dose escalation cohorts and the preferred dose and schedule of pamiparib plus TMZ has been determined. Approximately 200 patients will be enrolled in the dose expansion phase with approximately 20-25 patients enrolled into each cohort. Enrollment into each cohort will occur in parallel.

Expansion Cohort 1: Patients with platinum-sensitive high-grade epithelial, non-mucinous, ovarian cancer, fallopian cancer, or primary peritoneal cancer with either known deleterious or suspected deleterious germline or somatic *BRCA1/2* mutation or with DNA HRD.

Expansion Cohort 2: Patients with TNBC with either known deleterious or suspected deleterious germline or somatic *BRCA1/2* mutation or with DNA HRD who have received 0-1 prior platinum-containing treatment in any treatment setting and treated with ≤ 3 prior regimens.

Expansion Cohort 3: Patients with mCRPC with either known deleterious or suspected deleterious germline or somatic *BRCA1/2* mutation or with documented HRD.

Expansion Cohort 4: Patients with extensive-stage SCLC who have been treated with ≤ 2 prior regimens.

Expansion Cohort 5: Patients with gastric or gastroesophageal junction cancer who have been treated with ≤ 2 prior regimens.

Expansion Cohort 6: Patients with non-squamous and squamous NSCLC, esophageal cancer, squamous head and neck cancer, or soft tissue sarcomas (specific subtypes: undifferentiated pleomorphic sarcoma, leiomyosarcoma, malignant peripheral nerve sheath tumor, dedifferentiated liposarcoma, myxofibrosarcoma) whose tumors are HRD+ as determined centrally by the Myriad myChoice® HRD Plus assay. Patients with NSCLC, esophageal and head and neck cancer may have received at least 1 but no more than 3 prior lines of therapy. Patients with soft tissue sarcoma may have received at least 1 but no more than 3 prior lines of

therapy OR no therapy if, in the opinion of the investigator, standard of care first line therapy is not appropriate.

The safety and PK assessments, as well as the rules for continued dosing in the cohort-expansion phase, will be identical to those in the dose escalation phase.

Each cohort will be evaluated independently for study endpoints and can be closed due to lack of enrollment, anti-tumor activity or other reasons. Cohorts may be also further expanded based on clinical emerging data.

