11. STATISTICAL CONSIDERATIONS AND ANALYTICAL PLAN

All statistical analyses will be performed by the sponsor or designee after the study is completed and the database is locked and released. Details of the statistical analyses will be included in a separate statistical analysis plan (SAP).

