11.4. Sample Size Consideration

Approximately 250 patients (50 in the dose escalation phase and 200 in the dose expansion phase) will be enrolled. A sample size of 20-25 patients in an expansion cohort will provide the half width of the 90% confidence interval of the ORR approximately 13% to 20% when the observed ORR is approximately 40%. Hence, the low bound is above 20%. This is considered adequate in the preliminary assessment of anticancer activity of pamiparib and TMZ combination therapy. An expansion cohort can be further expanded to confirm efficacy.

Table 5: Estimated Objective Response Rate and 90% Confidence Interval for 20-25 Patients

Sample Size	No. of Responders	Response Rate	Confidence Interval	
			Lower Limit	Upper Limit
20	8	40%	22%	61%
21	8	38%	21%	58%
	9	43%	24%	63%
22	8	36%	20%	56%
	9	41%	23%	60%
23	9	39%	22%	58%
	10	43%	26%	62%
24	9	38%	21%	56%
	10	42%	25%	60%
25	10	40%	24%	58%

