11.5. Interim Analysis

No interim analysis is planned.

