7 INTERIM ANALYSIS

In dose escalation phase, before the dose is escalated to the next level, the safety review team will review the safety data to determine the next dose level. The recommended dose for dose expansion phase will be determined by the safety review team before the dose expansion phase.

Interim CSR may be conducted for the purpose of safety and/or efficacy review.

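### Cohorts may be closed or extended on response data although the Protocol plans no interim analysis, and a combined ORR in an extended cohort would reuse the responses that triggered the extension

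*SAP*

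**What the plan says.** **Closure.** SAP 5 and the Protocol synopsis: "Cohorts can be closed due to futility or clinical efficacy based on statistical evaluation". Protocol 4.3 says a cohort "can be closed due to lack of enrollment, anti-tumor activity or other reasons".

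**Extension.** SAP 5, in a separate sentence: "Cohorts can be also further expanded based on emerging data". Protocol 11.4 gives a purpose: "An expansion cohort can be further expanded to confirm efficacy".

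**Looks at the data.** Protocol 11.5: "No interim analysis is planned". Protocol 11: "All statistical analyses will be performed by the sponsor or designee after the study is completed and the database is locked and released". SAP 7, headed Interim Analysis, says: "Interim CSR may be conducted for the purpose of safety and/or efficacy review". SAP 2 (Study Overview) already sets its scope: "For the interim clinical study report (CSR), only cohort 1 to 5 will be included".

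**Reporting.** SAP 6 summarizes expansion data by cohort. SAP 6.3.1 gives ORR a two-sided exact binomial 90% CI per cohort. SAP 6 plans no formal hypothesis test, and SAP 6.2.4 plans no multiplicity adjustment.

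Neither document gives a time, a minimum number of patients or a criterion for closing or extending a cohort. SAP 8, which lists changes from the planned analysis, does not mention an efficacy review.

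**The concern.** Closing a cohort for futility or efficacy, or extending it to confirm efficacy, cannot be done without examining that cohort's responses while the study runs. The Protocol says this will not happen, and the SAP leaves room for it. A reader of the final report could not tell which cohorts were reviewed, when, or on what data.

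The second issue is the estimate. ORR is a primary endpoint, and nothing in the plan separates initial from extension patients. If a cohort is extended because its first 20-25 patients responded well, those responses count twice: once as the reason to extend, and again in the ORR offered as confirmation. The plan's own adequacy argument is that the lower limit lies above 20%. That limit is pushed up in a cohort selected this way.

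**Working it through.** **1. The plan's own intervals.** For x responders of n, the exact (Clopper-Pearson) 90% limits are the 5% quantile of Beta(x, n-x+1) and the 95% quantile of Beta(x+1, n-x). This gives 21.7-60.6% for 8/20, 19.6-56.1% for 8/22 and 23.6-58.3% for 10/25. SAP Table 1 prints 22-61, 20-56 and 24-58. All 20 limits in the table reproduce. They assume a fixed n and make no allowance for a review.

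**2. Room for extension.** The expansion phase plans about 200 patients in 6 cohorts of 20-25. The initial cohorts use 6 x 20 = 120 to 6 x 25 = 150, which leaves 50 to 80 places.

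**3. Effect of extending on response.** Let X1 ~ Bin(n1, p) be the initial responders, extend if X1 >= k, and let X2 ~ Bin(n2, p) be the extension responders. The reported value is (X1+X2)/(n1+n2) with its ordinary exact 90% CI. Every outcome was enumerated exactly. The values of k and n2 are assumptions, because the documents give none.

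One row worked through (22+25, k = 8, p = 20%): P(X1 >= 8) = 5.6%. Given extension, the mean initial ORR is 38.65%. The mean combined ORR is (22 x 0.3865 + 25 x 0.20)/47 = 13.50/47 = 28.7%.

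True ORR 20%:

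| Rule | P(extend) | Mean initial ORR if extended | Mean combined ORR if extended | CI coverage if extended | Coverage over all cohorts |
|---|---|---|---|---|---|
| 22+25, >=8/22 | 5.6% | 38.7% | 28.7% | 69% | 93.5% |
| 22+25, >=7/22 | 13.3% | 34.7% | 26.9% | 81% | 92.6% |
| 20+20, >=8/20 | 3.2% | 42.1% | 31.0% | 54% | 97.4% |
| 20+20, >=5/20 | 37% | 29.4% | 24.7% | 89% | 94.8% |

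In the last column, cohorts that are not extended are analysed at n1.

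Two variants at true 20% bracket these rules. 22+25 on >=5/22 gives 23.5% and 92% coverage. 25+25 on >=10/25 gives 30.9% and 53%, with an extension probability of 1.7%.

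**4. Higher true rates.** At a true ORR of 30%, the first three rules give mean combined ORRs of 35.2%, 33.6% and 37.0%, with coverage of 87%, 91% and 88%. The 25+25 variant gives 36.8% and 80%. At 40%, the four rules in the table give 41-44%, with coverage of 93-94%.

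**5. Extension patients alone.** X2 does not depend on the decision to extend, so its exact CI keeps its usual coverage: 92-96% across these settings.

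**The case against.** The strongest case against is that the conditional figures look worse than the risk they describe. At a true ORR of 20%, a cohort seldom passes the stricter rules. The chance that it is extended and its combined lower limit also exceeds 20% is 1.7%, 2.6% and 1.5% for the first three rules, all below the nominal 5%. Coverage over all cohorts is at or above 90%. Lenient rules give 89-92% coverage even after selection. The aim is a preliminary assessment with descriptive intervals and no test. All of this stands, and it limits the severity.

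Some stronger readings also fail. A reader might infer that a statistical evaluation governs extension; the documents tie it only to closure. A reader might infer that both documents rule out an efficacy look; only the Protocol does, and SAP 7 allows one. A reader might take pooling of initial and extension patients as stated; it is implied by reporting per cohort.

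It could also be said that the Protocol excludes only a formal interim analysis and leaves informal review open. But Protocol 11 places all statistical analyses after database lock, which does not fit closure on a statistical evaluation.

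Overall coverage does not answer the remaining point. The Protocol's stated purpose for extension is confirmation, and the person judging that sees only the cohorts that were extended.

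**Conclusion.** The point holds in limited form. The Protocol and SAP disagree on whether cohort response is reviewed during the study, and no section describes the review that closure and extension need. If extension follows good early response, and if initial and extension patients are combined as the per-cohort reporting implies, the combined ORR overstates the confirmation. Under the four tabulated rules the overstatement is about 5 to 11 percentage points at a true ORR of 20%. It is about 4 to 7 points at 30% under the three stricter rules, and 1 to 4 points at 40%. Coverage in extended cohorts can fall well below 90% when the rule is strict and the true rate low.

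A reader might conclude that the planned 90% CI is invalid in general, or that a type I error rate is inflated. The documents do not support either. No test is planned, and coverage over all cohorts, extended or not, stays about 91-97% under these extension rules. The size depends wholly on assumed rules. The change should be made, but the planned analysis is usable without it for cohorts that are not extended.

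**What to change.** Reconcile Protocol 11 and 11.5 with the synopsis, SAP 5 and SAP 7. State that cohort ORR is reviewed during the study for closure and extension decisions, and record the number evaluable and the number of responders at each review. No look time or threshold has to be invented for this; the record shows what each decision rested on.

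For any extended cohort, report ORR with its exact 90% CI for the extension patients beside the combined value. Base any statement that efficacy is confirmed on the extension patients. If the initial patients are also shown alone, label that estimate as selected: its mean is about 35-42% at a true ORR of 20% under the three stricter rules, further from the truth than the combined value.

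The cost is one paragraph and one or two table rows per extended cohort. The extension-only interval is wider: at an observed 40%, 8/20 gives 21.7-60.6%, against 26.9-54.2% for 16/40 combined.
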